Study Description	This is a retrospective analysis of the presence of chromosomal rearrangements involving MYC, BCL2 and BCL6 genes by FISH in a retrospective, single-center series of large B-cell lymphomas, in order to allow a better classifications of these cases according to the current WHO 2017 classification. If this evaluation will be confirmed as a reliable method to reclassify in different groups the evaluated tumors, it can be subsequently routinely apply to indicate the best treatment approaches in this high-risk setting of patients with a significant impact on patients' morbidity and mortality, and also on the health system and related costs.	
	Primary	Secondary
Objectives	
 1. To re-classify retrospective series of large B-cell lymphomas (LBCL) according to the current WHO 2017 classification by using FISH for the detection of MYC, BCL2 and BCL6 rearrangements. 2. To establish the association between re-classification of LBCL using FISH for the detection of MYC, BCL2 and 	
 1. To establish the association between re-classification of LBCL using FISH for the detection of MYC, BCL2 and BCL6 rearrangements and patients' outcomes. 2. To establish the association between re-classification of LBCL and risk of relapse. 3. To demonstrate that re-classification of LBCL exploiting FISH for the detection of MYC,

	BCL6 rearrangements and response to therapy.	BCL2 and BCL6 rearrangements is a reliable tool to support treatment decision plan. 4. To complete IHC analysis for further and/or novel pattern of antigen expression in HGBL. 5. To estimate the prevalence of MYC, BCL2 and BCL6 rearrangements/ amplifications detected by FISH in LBCL
Study Population	Adult subjects (> 18 years old) of any age and gender affected by large B-cell lymphoma. We expect to enroll around 555 subjects.	

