--	--

	Results will be summarized for each case and reported to the pathologist.
Planned Study Periods	Duration of the Enrollment period: 1 year Duration of the retrospective Follow-up: NA Duration of total study period: 1 year

ABBREVIATIONS AND DEFINITIONS

Abbreviations

BL	Burkitt lymphoma
CR	complete remission
DLBCL	diffuse large B-cell lymphoma
DOT	Duration of response
FISH	fluorescent in situ hybridization
HGBL	High-grade B-cell Lymphoma
IC	Informed Consent
I-FISH	Interphase Fluorescence In Situ Hybridization
IHC	immunohistochemistry
OS	Overall Survival
PFS	Progression-free Survival
PR	partial response

BACKGROUND

The 2017 WHO classification introduced the new clinical entity “High-grade B-cell Lymphoma” (HGBL), including large B-cell lymphomas with chromosomal rearrangements involving MYC gene (region 8q24) and BCL2 gene (region 18q21) (so called “double hit lymphoma”, representing 60% of HGBL) and/or BCL6 (region 3q27) (also called “triple hit lymphoma”, representing 20% of HGBL), identified by means of fluorescent in situ hybridization (FISH) and/or conventional cytogenetic analysis. HGBL replaced the old WHO 2008 category of ‘unclassifiable B-cell lymphoma with features intermediate between diffuse large B-cell lymphoma and BL’ and encompasses also diffuse large B-cell lymphoma (DLBCL) by morphology harboring MYC and BCL-2 and/or BCL-6 rearrangements.

Clinically, HGBL are characterized by adverse prognosis and poor response to standard treatments, such as R-CHOP regimen, with a median OS of 12 months or less. The role of

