We propose to retrospectively analyze the presence of chromosomal rearrangements involving MYC, BCL2 and BCL6 genes by FISH in a retrospective, single-center series of large B-cell lymphomas, in order to allow a better classifications of these cases according to the current WHO 2017 classification. If this evaluation will be confirmed as a reliable method to reclassify in different groups the evaluated tumors, it can be subsequently

routinely apply to indicate the best treatment approaches in this high-risk setting of patients with a significant impact on patients' morbidity and mortality, and also on the health system and related costs. Moreover, this study could give important information about the real incidence and predictive value of MYC, BCL2 and BCL6 rearrangements.

OBJECTIVES

Primary objectives:

1. To re-classify retrospective series of large B-cell lymphomas (LBCL) according to the current WHO 2017 classification by using FISH for the detection of MYC, BCL2 and BCL6 rearrangements.
2. To establish the association between re-classification of LBCL using FISH for the detection of MYC, BCL2 and BCL6 rearrangements and survival.

Secondary objectives:

1. To establish the association between re-classification of LBCL using FISH for the detection of MYC, BCL2 and BCL6 rearrangements and patients' response to treatments.
2. To establish the association between re-classification of LBCL and risk of relapse.
3. To demonstrate that re-classification of LBCL exploiting FISH for the detection of MYC, BCL2 and BCL6 rearrangements is a reliable tool to support treatment decision plan.
4. To complete IHC analysis for further and/or novel pattern of antigen expression in HGBL.
5. To estimate the prevalence of MYC, BCL2 and BCL6 rearrangements/amplifications detected by FISH in LBCL
6. To describe the main treatment patterns according to disease characteristics.

THERAPEUTIC OUTCOME

Primary outcome:

1. Overall Survival (OS)

Secondary outcome:

1. Progression-free Survival (PFS)
2. Overall Response Rate (ORR; partial response [PR] + complete remission [CR])
3. Duration of response (DOR; partial response [PR] + complete remission [CR])
4. Relapse rates and patterns
5. Incidence of MYC, BCL2 and BCL6 rearrangements in LBCL

STUDY DESIGN

Single center, retrospective observational, pharmacological and of molecular characterization study.

Study duration 1 year

STUDY POPULATION

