Interphase Fluorescence In Situ Hybridization (I-FISH) for detection of MYC, BCL2 and BCL6 rearrangements will be performed on the previously histologically reviewed large B-cell lymphoma cases. A "split-apart" FISH approach will be used: the chosen probes for each gene of interest consist of two direct labelled gene locus regions (green and orange), hybridizing distal and proximal to the gene breakpoint and separation/fusion of the two signals will indicate presence/absence of the rearrangements. Three 4 μ m tissue sections will be prepared for each sample, they will be pretreated according to the Zytolight FISH-Tissue Implementation Kit protocol (Zytovision, GmbH). Hybridization will be then carried out overnight on a Thermobrite hybridizer (Euroclone), using the Zytolight SPEC MYC Dual Color Break Apart Probe, Zytolight SPEC BCL2 Dual Color Break Apart Probe, Zytolight SPEC BCL6 Dual Color Break Apart Probe, following the manufacturer protocol; the next day, after unbound probes are removed by stringency washing steps, the slides will be counterstained with DAPI. Hybridized probes will be visualized using a fluorescence microscope (AxioImager Z2, Zeiss) equipped with excitation and emission filters specific for the fluorochromes by which the FISH probes are directly labeled. FISH semiautomatic analysis will be performed using the Metafer4 software (Metasystems): FISH signals will be counted in 200 interphase nuclei from at least 4 to 8 areas selected for well-preserved cellular and nuclear morphology to ensure representative sampling and to avoid nuclear truncation artifacts; a signal split, which indicates gene rearrangement, will be counted when the distance between splitted green and orange signals is ≥ 2 of the estimated signal diameter. The already defined laboratory cutoff for gene rearrangements will be used (2%

for all the used probes). Results will be summarized for each case and reported to the pathologist.

STUDY VARIABLES

Conventional anographic variables, findings of histopathological diagnosis, results of IHC and FISH analyses, staging, therapeutic management and outcome will be considered.

DATA MANAGEMENT

Data Recording and Record-Keeping

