Clinical characteristics and response rates of the therapeutic subgroups will be compared using the α_2 test or Fisher exact test for categorical variables, according to the sample size. Factors potentially conditioning outcome will be assessed by α_2 test and logistic regression. Survival curves will be generated by the Kaplan-Meier method. Overall survival (OS) will be calculated from the date of pathologic diagnosis to death or to the last date of follow-up, while progression-free survival (PFS) will be calculated from the first day of treatment to relapse, progression or death, or to the last date of follow-up. Survival rates will be reported as 2-year OS and 95% CI. Impact on survival of clinical and therapeutic variables will be evaluated by comparing the entire OS curves by means of the log-rank test.

The independent prognostic value of variables will be analyzed using the Cox model. The year of diagnosis will be included as a continuous variable in the multivariate analyses to exclude the possibility that modern medical management could influence outcome more than the treatment itself. Backward stepwise regression will be performed to identify the most powerful predictors of survival. All the probability values will be two-sided. Statistical analysis will be performed with Statistical software (Statistica 10.0, Tuxon, AZ, USA) on a unique database including clinical and pathological data on an estimated sample size of 555 patients.

ETHICAL CONSIDERATIONS AND INFORMED CONSENT

The Investigator and all study staff will ensure that the clinical study is conducted in accordance with good clinical practice and institutional requirements, including those for subject privacy, Ethics Committee approval and record retention, and with the Declaration of Helsinki (revised October 2008) and in compliance with principles defined in the Determinazione of the Agenzia Italiana del Farmaco, dated 20 March 2008. The protocol, being retrospective, will be notified to the IEC of the IRCCS San Raffaele Scientific Institute

of Milan. In the context of clinical practice, patients already provided consent to use of health data for research purposes.

PATIENT SAFETY

Given the observational retrospective nature of the study, for the patients enrolled in this study, there are no additional physical, psychological, or social adverse effects compared to the standard of care clinical practice.

FINANCE AND INSURANCE

The study is non-profit in nature.

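### The survival analysis never names FISH class, the primary exposure, and leaves it open to removal by backward stepwise selection

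*Protocol*

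**What the plan says.** The Objectives section of the protocol body gives as primary objective 2: "To establish the association between re-classification of LBCL using FISH for the detection of MYC, BCL2 and BCL6 rearrangements and survival". The Therapeutic Outcome section names OS as the primary outcome. The synopsis words the same objective differently, ending in "BCL6 rearrangements and response to therapy".

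The Study Variables section lists FISH among the data collected: "results of IHC and FISH analyses, staging, therapeutic management and outcome will be considered". It gives FISH no role in any model.

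The section Statistical Considerations and Analysis Plan then sets out the methods:

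- Response: "Clinical characteristics and response rates of the therapeutic subgroups will be compared".
- Survival, univariate: "Impact on survival of clinical and therapeutic variables will be evaluated by comparing the entire OS curves by means of the log-rank test".
- Survival, multivariable: "The independent prognostic value of variables will be analyzed using the Cox model". Year of diagnosis is to be included as a continuous covariate; no other term is named.
- Model building: "Backward stepwise regression will be performed to identify the most powerful predictors of survival".

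Neither FISH, the three genes nor the re-classified groups appear in that section. No removal threshold is given for the stepwise procedure.

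**The concern.** The objective concerns one exposure, FISH class, and its relation to one outcome. The statistical section is organised around treatment groups and an open list of predictors. Even the reason given for including year of diagnosis is to separate it from the effect of treatment, not from that of FISH class.

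Backward selection suits a search for predictors. It does not suit the estimation of a named effect. If FISH class is one candidate among others, there are two possible outcomes. It may be eliminated, and the final model then says nothing quantitative about the primary question. Or it may survive, and its HR is then reported conditional on significance: too far from 1 on average, with a confidence interval that ignores the selection. The protocol wants re-classification to support treatment decisions, so a missing or inflated HR matters.

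**Working it through.** **What can be reproduced.** The protocol gives a sample size of 555 without an event count, FISH-class prevalence, target HR, alpha or power. There is no stated calculation to check. The figures below show how much the selection rule could matter.

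**Inputs.** From the protocol: n = 555. Assumed: 40% deaths, so D = 0.40 × 555 = 222; FISH-positive share p = 0.08; a term is kept if two-sided p<0.05.

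**Analytic approximation (Schoenfeld).**

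- SE of the log HR = 1/√(D·p·(1−p)) = 1/√(222 × 0.08 × 0.92) = 1/√16.3 = 0.247.
- Chance kept = P(|Z| > 1.96), where Z is normal with mean ln(HR)/SE and variance 1.
- Mean HR when kept = exp(SE × mean of Z given |Z| > 1.96).

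For HR 1.5, the mean of Z is 0.405/0.247 = 1.64. The chance kept is P(N(0,1) > 1.96 − 1.64) = 0.37. The mean of Z when kept is 1.64 + 0.379/0.374 = 2.65, so the mean HR when kept is exp(2.65 × 0.247) = 1.93.

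| True HR | Chance kept | Mean HR when kept |
|---|---|---|
| 1.3 | 0.19 | 1.84 |
| 1.5 | 0.37 | 1.93 |
| 2.0 | 0.80 | 2.18 |
| 2.5 | 0.96 | 2.56 |
| 3.0 | 0.99 | 3.01 |

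**Range.** With 167 to 278 deaths (30% to 50%) and 5% to 12% prevalence:

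- HR 1.5 is kept 0.21 to 0.59 of the time, with mean kept HR from 2.43 down to 1.69.
- HR 2.0 is kept 0.50 to 0.96 of the time, with mean kept HR from 2.66 down to 2.03.

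A looser threshold (removal at p>0.10) lowers the drop rate. At HR 1.5 it is still 22% to 69% over 5% to 15% prevalence and 166 to 278 deaths.

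**Simulated backward selection.** 2000 data sets per HR, n = 555, 40% deaths, 8% FISH-positive. Year of diagnosis was locked in. FISH class and six assumed covariates (age, stage, LDH, performance status, Hans class, sex) were eliminated backward at p<0.05. The comparator is the same Cox model with every term forced in.

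| True HR | Kept | Mean HR when kept | 95% CI coverage when kept | Forced: mean HR | Forced: coverage |
|---|---|---|---|---|---|
| 1.3 | 0.225 | 1.77 | 0.85 | 1.31 | 0.95 |
| 1.5 | 0.426 | 1.85 | 0.90 | 1.51 | 0.94 |
| 2.0 | 0.870 | 2.12 | 0.97 | 2.04 | 0.95 |
| 2.5 | 0.979 | 2.52 | 0.95 | 2.54 | 0.94 |

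A separate simulation at HR 1.5 agreed: about 46% kept, mean HR 1.81 against 1.49 forced, coverage 0.89 when kept.

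**Does the protocol fix the HR?** No. The Background describes HGBL under standard treatment "with a median OS of 12 months or less", and 5-year OS of 66% in HGBL under the intensified regimen. Under exponential survival the hazards are ln 2/1 = 0.693 and −ln(0.66)/5 = 0.083 per year, a ratio of 8.3. Both figures concern HGBL, and no OS figure is given for the other cases. The HR for FISH class in a series of mixed regimens therefore cannot be read from the document.

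**The case against.** Much of this describes detail that a protocol may leave to a separate SAP, and only the protocol is at hand. The Cox sentence and the stepwise sentence are separate, so a full Cox model containing FISH class is not ruled out. The objective asks for an association, which a log-rank test by FISH class could show without any selection step. The Histopathology and Immunohistochemistry text also says that FISH-defined high-grade cases will be related to clinical parameters and treatment response.

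These points limit the finding but do not remove it. A full Cox model or a log-rank test by FISH class is permitted but not promised. The text on high-grade cases covers response, not survival. The protocol also goes beyond silence: it fixes a data-driven selection rule and guarantees one covariate a place, but not the primary exposure.

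On size, the objection has more force. Every input except 555 is assumed. At HR 2.0 the analytic bias is about 9% (2.18/2.0), but the simulation shows about 4% (2.12/2.04) and no loss of coverage. The hazard comparison is weak evidence: the 66% comes from 22 HGBL patients in a series that included HIV-positive patients, whereas this study requires HIV negativity. It shows only that the protocol does not settle the HR.

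**Conclusion.** The concern holds and should be fixed. That the statistical section gives the primary exposure no role, and does not protect it from backward selection, is plain from the text and rests on no assumption. The consequence depends on the true HR, the number of deaths and the prevalence of the FISH-positive class. Upward bias is material at a true HR of about 1.5 or below and negligible from 2.5. At 2.0 it is small in the base case but larger when the class is rare and deaths are few. The chance of being kept is essentially the power of the study, which no rewording will raise. What can be removed is the reporting filter and the bias it brings.

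**What to change.** 1. Reconcile primary objective 2 between the synopsis (response) and the body (survival).
2. State that FISH class is the grouping variable for the primary Kaplan-Meier and log-rank analysis of OS. The class could be WHO 2017 HGBL with MYC plus BCL2 and/or BCL6 rearrangement against the rest; any other grouping should also be fixed in advance.
3. Pre-specify one Cox model with FISH class, year of diagnosis (as already planned) and collected baseline prognostic factors, such as age and stage, all forced in. Report the FISH HR and 95% CI whatever the p-value.
4. Keep backward selection only as a labelled exploratory analysis, with FISH class and year of diagnosis locked in.
5. Add first-line regimen only as a sensitivity analysis. The Background indicates that regimen may have been chosen partly on MYC status, so adjusting for it changes the question.
6. If response is retained as the primary association, apply the same rule to the logistic model.

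The cost is analysis-plan wording; no further patients, samples or assays are needed. The model spends a few more degrees of freedom, which roughly 170 to 280 assumed deaths can carry. The FISH HR may be reported with a wide interval: exp(1.96 × 0.247) = 1.62, a factor of about 1.6 either way at 222 deaths and 8% prevalence.
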